6.2 Evaluations on Treatment

Collection of Concomitant Medications and Adverse Events (AEs) should occur throughout the study, as described. Pre-treatment (Screening) evaluations do not need to be repeated if within 28 days of Cycle 1 Day 1.

Day 1 (±3 days)

- History and physical exam with vital signs
- Labs: CMP, CPK, CBC with differential (diff), Uric acid, Urinalysis
- If WOCBP, pregnancy test within 3 days of treatment for Cycle 1 only
- AEs

- ECG (if clinically indicated)
- Study drugs to be taken daily at the same time every day for 21-consecutive days.
- CA-125
- Lipid panel (total cholesterol, HDL, LDL, triglycerides) fasting preferred
- Coagulation (PT and INR)

Day 21 (±3 days)

- Ribociclib –start of 1-week off period.
- Letrozole Continue taking through the week off period of Ribociclib.
- 6.3 Off-Treatment Evaluations (End of Treatment or EOT visit)

The end of treatment visit will be performed as soon as possible but no later than 4 weeks (i.e., 28 days) $\pm 7 \text{ days}$ from last dose of investigational product and prior to the initiation of any new anticancer therapy.

6.4 Follow-up Evaluations

After discontinuation of study treatment, post-study survival status (including post study anticancer therapies) will be collected approximately every 3 months for the first two years and then every six months for the next three years. from the last dose of study treatment. Telephone contact is acceptable.

If patient comes off study treatment prior to progression, continue tumor measurements and radiologic evaluations on schedule until progression or initiation of a subsequent cancer therapy. Toxicity assessments will be continued until resolution or return to baseline. Patients will be followed after last drug dose until toxicity resolution or return to baseline, until progression if patient withdraws before progressive disease, or until study withdrawal if it occurs before this time.

Patients who discontinue study treatment for reasons other than radiographically and/or clinically (i.e., for photographed or palpable lesions) documented disease progression as per RECIST v1.1 definitions will continue to have tumor assessment performed during the follow-up visits every 3 months (± 7 days) from the date of starting protocol therapy until disease progression, initiation of new anticancer therapy or discontinuation of patient from overall study participation (eg, death, patient's request, lost to follow-up), whichever occurs first.

6.5. Schedule of Assessments

	Screening Phase ^a	• •			Post Treatment Follow up Phase ^e		
Visit Name	Screening	Cycle 1*	Cycle 2	Cycle 3	Cycle 4 - n	End of Treatment	
Treatment Days	Prior to Day 1	1	1	1	1		
Physical Assessments							
History & Physical Exam with vital signs	Х	Х	Х	Х	X		
Review of Concomitant Medications			Continuous	- up to 30	days after last	t dose of study treatm	nent
Performance Status	Х						
Laboratory Assessments							
Hematology: CBC	Х	X	X ^g	Xg	Xg	X	
Chemistry (including LFTs): K, Ca, Mg, Na, P, CPK, Uric Acid, AST, ALT, total bilirubin, BUN	Х	Х	Х	Х	Х	Х	
Coagulation: PT and INR	Х	Х	Х	Х	Х	Х	
Lipid Panel: Total cholesterol, HDL, LDL, triglycerides (fasting preferred)	Х	Х			X ^h		
CA-125	Х	Х	Х	Х	Х		Х

	Screening Phase ^a		Treatment Phase: 28-day cycles ^f			Post Treatment Follow up Phase ^e	
Visit Name	Screening	Cycle 1	Cycle 2	Cycle 3	Cycle 4 - n	End of Treatment	
Urinalysis	Х	Х	Х	Х	Х	X	
Urine Pregnancy Test (WOCBP only)	Х	Х					
Cardiac Assessments							
ECG (12-Lead) ^j	Х	X ⁱ X ⁱ As clinically indicated					
Safety & Imaging	•						
Toxicity Assessment/Adverse Events					Continuous		
Tumor Imaging ^b	Х			X _q			Х
H&E for Pathology Review ^c	Х				'		
Survival Follow Up							Х

Legend:

- * Pre-treatment (Screening) evaluations do not need to be repeated if within 28 days of Cycle 1 Day 1.
- a. Within 28 days of first dose of letrozole + ribociclib
- b. CT or MRI of chest, abdomen, and pelvis
- c. H&E stained slide must be submitted for pathology review to confirm eligibility
- d. Every 3 cycles
- e. The end of treatment visit will be performed as soon as possible but no later than 4 weeks (i.e., 28 days) ± 7 days from last dose of investigational product and prior to the initiation of any new anticancer therapy. After discontinuation of study treatment, post-treatment follow-up, including survival status, will be collected every 3 months for the first 2 years and then every 6 months for 3 year for a total of 5 years. Telephone contact is acceptable. If patient comes off study treatment prior to progression, continue tumor measurements and radiologic evaluations on schedule until disease progression or initiation of a subsequent cancer therapy. Toxicity assessments continue until resolution or return to baseline. Patients who discontinue study treatment for reasons other than disease progression should have tumor assessments performed during follow-up visits every 3 months until disease progression, initiation of new anticancer therapy or discontinuation from participation on study.

- f. Due to scheduling, these visits may occur +/- 3 days from the required time point. Additionally, it may be necessary to perform these procedures at unscheduled time points if deemed clinically necessary by the Investigator or in order to accommodate patient/physician scheduling logistics.
- g. Must be performed within 3 days of re-treatment.
- h. Every 4th cycle
- i. Predose and 2-4 hours postdose at investigator's discretion if clinically indicated.
- j. For patients with QTcF ≥ 481 ms at any time, interrupt study treatment and follow the procedures described in the "Ribociclib Dose Modification section". If treatment is resumed, repeat ECGs 7 days and 14 days after dose resumption (and then as clinically indicated). During subsequent cycles, perform predose ECG for every cycle starting at cycle 6, and predose and 2-4 postdose starting at cycle 9 and every 3rd cycle thereafter.

7.0 PATHOLOGY/BIOSPECIMEN REQUIREMENTS

7.1 Pathology Review for Confirmation of Eligibility

This protocol requires a digital pathology review to confirm eligibility.

Regardless of whether the patient's original diagnosis was ovarian or peritoneal serous tumor of low malignant potential or low-grade serous carcinoma, eligible patients include those with recurrent low-grade serous carcinoma of the ovary, fallopian tube or peritoneum.

One H&E stained slide from the recurrent tumor (obtained at secondary surgery, prior biopsy, or SOC image-guided fine needle/core biopsy) or from the original diagnostic specimen documenting low-grade serous carcinoma must be obtained from the pathology department and sent by overnight courier at the institution's expense to the Biopathology Center:

GOG 3026 Pathology Review Biopathology Center Nationwide Children's Hospital [name] [name]

[contact] [contact]

Email: [contact]

A completed copy of the Digital Pathology Screening Form (Appendix E), printout of the IRT Screening Confirmation, and a copy of the corresponding pathology report must be submitted with the H&E. All items shipped must be labeled with the Screening ID (format: XXXX-3026-YYYY; see Section 6.1 for details). Slides must also be labeled with the surgical pathology accession number and block number from the corresponding pathology report.

7.2 Protocol for digital review of pathology slides

The representative H&E stained slide will be scanned at the Biopathology Center into a tissue review database. A gynecologic pathologist will be provided the case for central prospective review using VIPER (Virtual Imaging for Pathology Education and Research). The institution will be notified of patient eligibility by email within five business days of:

- (1) receipt at the Biopathology Center of the
 - a. H&E,
 - b. corresponding pathology report,
 - c. completed Digital Pathology Screening Form (Appendix E), and
 - d. printout of the IRT Screening Confirmation; and
- (2) pathologist review.

Failure to send the required materials and/or improper labelling could delay the results review.

7.3 Translational Research

Next generation sequencing will be performed on all pre-treatment tissue specimens. These results will be correlated to response and clinical benefit. In addition, we will evaluate estrogen receptor (ER) signaling and correlate these findings with response.

Specimen Requirements

If the patient gives permission for her specimens to be collected and used for this optional translational research component, then participating institutions are required to submit the patient's translational research specimens as outlined below (unless otherwise specified). **Refer to Appendix F for details.**

Required Specimen (Specimen Code)	Collection Time Point	Ship To		
FFPE Tumor Tissue (Submit at least one tumor type – Listed in order of preference)				
Archival FFPE Recurrent Primary (FRP01) or Recurrent Metastatic (FRM01) Tumor ¹				
1st Choice: block	Prior to study treatment			
2nd Choice: 20 unstained slides (10 charged, $5\mu m$ & 10 uncharged, $10\mu m$)		Biopathology Center within 8 weeks of		
Archival FFPE Primary (FP01) or Metastatic (FM01) Tumor ¹		registration ²		
1st Choice: block	Prior to all treatment			
2nd Choice: 20 unstained slides (10 charged, $5\mu m$ & 10 uncharged, $10\mu m$)				
Whole Blood (WB01) 7-10mL drawn into purple top (EDTA) tube(s) and frozen ³	Prior to starting study treatment	Biopathology Center within 1 week of registration ²		

- 1 A copy of the corresponding pathology report must be shipped with all tissue specimens sent to the Biopathology Center.
- 2 Biopathology Center / Protocol GOG 3026, Nationwide Children's Hospital, [name], [name], [contact], [contact], Email: [contact]
- 3 Do not use glass blood collection tubes.

7.4 Laboratory Testing

7.41 Hormone Receptor Immunohistochemistry

Unstained sections of formalin-fixed, paraffin-embedded (FFPE) tumor will be used for hormone receptor (e.g., estrogen receptor [ER]-alpha, ER-beta, progesterone receptor [PR]-alpha, PR-beta, G protein-coupled ER [GPR-30]) immunohistochemistry (IHC).

7.42 Mutation Analysis

Unstained sections of FFPE tumor and DNA extracted from whole blood will be used for mutational analysis (e.g., PTEN, PIK3CA, KRAS, CTNNB1 [beta-catenin], Rb).

7.43 Next-Generation Sequencing (NGS)

Unstained sections of FFPE tumor will be used for next-generation sequencing (NGS) mutational analysis.

8.0 Evaluation Criteria

8.1 Antitumor Effect – Solid Tumors

Response and progression will be evaluated in this study using the Response Evaluation Criteria in Solid Tumors (RECIST) guideline (version 1.1) [Eur *J Ca* 45:228-247, 2009]. Changes in the largest diameter (unidimensional measurement) of the tumor lesions and the shortest diameter in the case of malignant lymph nodes are used in the RECIST criteria.

In the present study, tumors will be re-evaluated by CT scan of the chest, abdomen, and pelvis every 12 weeks during treatment and at least 4 weeks after the first observation of a complete or partial response. After discontinuation of protocol treatment, patients who have not progressed will still be re-evaluated every 12 weeks.

8.1.1 Definitions

Evaluable for toxicity. All patients will be evaluable for toxicity from the time of their first treatment with ribociclib and letrozole

Evaluable for objective response. Only those patients who have measurable disease present at baseline, have received at least one cycle of therapy, and have had their disease re-evaluated will be considered evaluable for response. These patients will have their response classified according to the definitions stated below. (Note: Patients who exhibit objective disease progression prior to the end of cycle 1 will also be considered evaluable.)

Evaluable Non-Target Disease Response. Patients who have lesions present at baseline that are evaluable but do not meet the definitions of measurable disease, have received at least one cycle of therapy, and have had their disease re-evaluated will be considered evaluable for non-target disease. The response assessment is based on the presence, absence, or unequivocal progression of the lesions.

Disease Parameters

Measurable disease. Measurable lesions are defined as those that can be accurately measured in at least one dimension (longest diameter to be recorded) as \geq 20 mm by chest x-ray, as \geq 10 mm with CT scan, or \geq 10 mm with calipers by clinical exam. All tumor measurements must be recorded in millimeters (or decimal fractions of centimeters).

Note: Tumor lesions that are situated in a previously irradiated area might or might not be considered measurable. If the investigator thinks it appropriate to include them, the conditions under which such lesions should be considered must be defined in the protocol.

Malignant lymph nodes. To be considered pathologically enlarged and measurable, a lymph node must be \geq 15 mm in short axis when assessed by CT scan (CT scan slice thickness recommended to be no greater than 5 mm). At baseline and in follow-up, only the short axis will be measured and followed.

Non-measurable disease. All other lesions (or sites of disease), including small lesions (longest diameter <10 mm or pathological lymph nodes with ≥ 10 to <15 mm short axis), are considered non-measurable disease. Bone lesions, leptomeningeal disease, ascites, pleural/pericardial effusions, lymphangitis cutis/pulmonitis, inflammatory breast disease, and abdominal masses (not followed by CT or MRI), are considered as non-measurable.

Note: Cystic lesions that meet the criteria for radiographically defined simple cysts should not be considered as malignant lesions (neither measurable nor non-measurable) since they are, by definition, simple cysts.

'Cystic lesions' thought to represent cystic metastases can be considered as measurable lesions, if they meet the definition of measurability described above. However, if non-cystic lesions are present in the same patient, these are preferred for selection as target lesions.

Target lesions. All measurable lesions up to a maximum of 2 lesions per organ and 5 lesions in total, representative of all involved organs, should be identified as **target lesions** and recorded and measured at baseline. Target lesions should be selected on the basis of their size (lesions with the longest diameter), be representative of all involved organs, but in addition should be those that lend themselves to reproducible repeated measurements. It may be the case that, on occasion, the largest lesion does not lend itself to reproducible measurement in which circumstance the next largest lesion which can be measured reproducibly should be selected. A sum of the diameters (longest for non-nodal lesions, short axis for nodal lesions) for all target lesions will be calculated and reported as the baseline sum diameters. If lymph nodes are to be included in the sum, then only the short axis is added into the sum. The baseline sum diameters will be used as reference to further characterize any objective tumor regression in the measurable dimension of the disease.

Non-target lesions. All other lesions (or sites of disease) including any measurable lesions over and above the 5 target lesions should be identified as **non-target lesions** and should also be recorded at baseline. Measurements of these lesions are not required, but the presence, absence, or in rare cases unequivocal progression of each should be noted throughout follow-up.

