11.0 Statistical Considerations

The intent of this this study is to assess the anti-tumor activity of the combination of letrozole + ribociclib in women with recurrent low-grade serous carcinoma of the ovary, fallopian tube or peritoneum measured by objective tumor response. This is a single-arm, open-label phase II study with a safety lead-in using an optimal flexible 2-stage design (33).

The targeted accrual for the first stage of the study will be 23 eligible and evaluable patients but permitted to range from 19 to 26 for administrative reasons. The cumulative targeted accrual for the second stage will be 48 eligible and evaluable patients but permitted to range from 44 to 51 for administrative reasons.

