Table 11.1: Posterior Probabilities of θ [Pr(DLT)] Exceeding the Target of 0.25 and Corresponding Critical Values for Consideration of Stopping for Toxicity

X					Pr(θ > 0.25	x,n)				
n	0	1	2	3	4	5	6	7	8	9	10
6	0.13	0.33	0.58	0.79	0.92	0.98	0.99				
7	0.10	0.28	0.52	0.74	0.89	0.96	0.99	1.00			
8	0.08	0.24	0.46	0.69	0.85	0.94	0.98	1.00	1.00		
9	0.06	0.20	0.41	0.63	0.81	0.92	0.97	0.99	1.00	1.00	
10	0.05	0.16	0.35	0.57	0.77	0.89	0.96	0.99	1.00	1.00	1.00

Phase II

The intent of this study is to assess the anti-tumor activity of the combination of letrozole + ribociclib measured by objective tumor response. Tumor response is dichotomized as response (i.e., complete or partial response) vs. non-response (i.e., stable disease, progressive disease, or unknown) and is assumed to have a Bernoulli distribution with a probability equal to π . Given a sample size, the number of tumor responses is binomially distributed with a given sample size and probability equal to π . Statistically, the evaluation of the study regimen efficacy measured by tumor response will be formulated through hypothesis testing via tumor response.

If combination proposed here has a true response rate of 10% or less, it would be considered of little clinical significance. Alternatively, if the true response rate were at least 25%, further investigation would be clearly indicated. Therefore, the primary hypotheses for this study can be formulated as follow:

H0: π ≤ 0.10,

H1: π ≥ 0.25,

where π is the probability of true tumor response, H0 is the null hypothesis and H1 is the alternative hypothesis. An optimal flexible two-stage design will be implemented to evaluate the primary hypotheses with average type I and type II error rates at 0.1 level, respectively (33). This design has early stopping guidelines that intends to limit patient accrual to inactive treatments and it permits the actual number of patients entered in each stage to vary slightly in order to

accommodate the challenges of coordinating a multicenter clinical trial while maintaining the levels of average type I and type II errors.

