We will target an accrual of 23 eligible and evaluable patients in the first stage of this study, but in practice permit accrual to range from 19 to 26 patients due to administrative coordination. If there are more than 2 out of 19-25, or 3 out of 26 patients responding (complete or partial response) and medical judgment indicates, accrual to the second stage of the trial will be initiated. Otherwise, the study will be stopped and the treatment regimen will be classified as clinically uninteresting. If the study advances to the second stage, then an overall study accrual of 48 eligible and evaluable patients will be targeted, but permitted to range from 44 to 51 patients for administrative reasons. If more than 6 out of 44-45 patients respond or 7 out of 46-51 patients respond then the regimen will be considered worthy for additional investigation.

Under the assumed accrual ranges of 19 to 26 (stage 1) and 44 to 51 (cumulatively after stage 2), if the true probability of response is 10% (H0), then this study has a 64% probability of early termination and a probability of 10% of incorrectly declaring the study regimen interesting; if the true probability of tumor response is 25%, then the study has a 90% chance of correctly classifying the study regimen as being interesting.

The following table summarizes the accrual and decision guideline.

Stage of	Targeted	Limits of Actual	Max Number of Responses to
Accrual	Cumulative Accrual	Accrual	Reject Study Regimen
1	23	19-26	2/(19-25), 3/26
2	48	44-51	6/(44-45), 7/(46-51)

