11.4 Secondary and exploratory analyses

Secondary analyses

The proportion of patients who have clinical benefit will be calculated and an estimate of 90% confidence interval will be provided.

The frequency and maximum severity of acute adverse events will be tabulated graded by CTCAE v5.0.

Kaplan-Meier median estimates and graphs will be used to describe PFS and OS survival functions.

Exploratory analyses

Summary statistics (and graphs where it is appropriate) will be done for exploratory biomarker endpoints.

Appropriate methods will be implemented to explore the associations of biomarkers with the response and clinical benefit, e.g., Spearman's correlation coefficient for interval/ordinal type of

biomarker measurements with response or clinical benefit, chis-squared test for nominal type of biomarker measurements with response or clinical benefit.

The purpose of exploratory objective is to explore and possibly generate hypotheses for future study. Therefore there will be no adjustment for multiple tests.

11.5 Only those patients who are deemed "ineligible" or who receive no therapy will be eliminated from the analysis. All patients who receive any therapy will be evaluated for both treatment efficacy and toxicity. While on occasion, circumstances may prevent the determination of treatment efficacy, such patients will be included in the analysis and labeled as "unknown". This category will be listed and be reflected in the calculation of the response rate.

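### The go/no-go cutoffs are counted in evaluable patients as 8.1.1 defines them, but 11.5 keeps every eligible treated patient in the response rate, so the primary decision has two denominators

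*Combined protocol and SAP*

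**What the plan says.** **Stage sizes and cutoffs.** Section 11.0 says "The targeted accrual for the first stage of the study will be 23 eligible and evaluable patients", with a permitted range of 19–26. Section 11.3 repeats this and adds, for the second stage, "then an overall study accrual of 48 eligible and evaluable patients will be targeted", with a range of 44–51. The cutoffs are given over those same counts. Stage 1 continues "If there are more than 2 out of 19-25, or 3 out of 26 patients responding". The regimen is worth further study "If more than 6 out of 44-45 patients respond or 7 out of 46-51 patients respond". The table in 11.3 gives these figures as the largest numbers of responses that still reject, so the requirement is more than 3 of 26 and more than 7 of 46–51.

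**Who is evaluable.** Section 11 does not define the term for response. Section 8.1.1 does: "Only those patients who have measurable disease present at baseline, have received at least one cycle of therapy, and have had their disease re-evaluated". It adds one exception: "Patients who exhibit objective disease progression prior to the end of cycle 1 will also be considered evaluable".

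**Who is analysed.** In 11.5, only patients who are ineligible "or who receive no therapy will be eliminated from the analysis". Everyone else who received any therapy is assessed for efficacy, and patients whose response cannot be determined are labelled unknown and enter the response rate. The model in 11.3 agrees, since it sets response against "non-response (i.e., stable disease, progressive disease, or unknown".

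**The concern.** Take an eligible patient who starts treatment, stops before the first 12-week scan without objective progression, and is never re-imaged. Under 8.1.1 she is not evaluable and does not count towards 23 or 48. Under 11.5 she stays in the denominator as a non-responder. No passage says which set supplies n for the cutoffs.

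The two readings differ in a known direction. Section 8.1.3.4 allows a response to be claimed only if it is confirmed at least 4 weeks later, so patients without re-evaluation are in practice non-responders. Dropping them can only raise the observed rate. Because the cutoff changes between 45 and 46 patients (and between 25 and 26 at stage 1), the same data can fail under one passage and succeed under the other. The trial is single-arm and open-label, so responses are visible as they accrue, and an unsettled denominator could be settled after they are known.

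**Working it through.** **Inputs.** From 11.3: p0 = 0.10, p1 = 0.25, and average type I and II error of 0.10 each. Maximum responses to stop at stage 1: r1 = 2 for n1 = 19–25, 3 for n1 = 26. Maximum responses to reject at the end: r2 = 6 for n = 44–45, 7 for n = 46–51. The share d of eligible treated patients who are not evaluable under 8.1.1 is not given; d = 2%, 5%, 10% and 15% are assumed.

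**1. Reproduce the plan's figures.** With exact binomials, X1 ~ Bin(n1, p) and X2 ~ Bin(n − n1, p):

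- P(stop early) = P(X1 ≤ r1)
- P(declare active) = Σ over x > r1 of P(X1 = x) · P(X2 > r2 − x)

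The results are averaged with equal weight over the 8 × 8 = 64 permitted (n1, n) pairs.

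| | Stated | Average | At 23/48 |
|---|---|---|---|
| Early stop, p = 0.10 | 64% | 63.6% | 59.2% |
| Type I error | 10% | 9.88% | 9.05% |
| Power, p = 0.25 | 90% | 90.0% | 91.1% |

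The stated figures hold. Over single pairs, type I error runs from 6.6% to 14.5%. The design arithmetic is sound; what is unclear is which patients make up n.

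**2. Same data, two conclusions.**

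- Final: 48 treated, 3 not evaluable, 7 responders. 7/48 rejects (7 ≤ 7); 7/45 succeeds (7 > 6).
- Final: 46 treated. One or two non-evaluable patients are enough, because 7/46 rejects while 7/45 and 7/44 succeed.
- Stage 1: 26 treated, 1 not evaluable, 3 responders. 3/26 stops; 3/25 continues. At the target of 23 the cutoff stays at 2 while the evaluable count is at least 19.

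**3. How often the final conclusion flips.** Here the number treated is fixed and there is no replacement. Each patient is a responder (p), not evaluable (d) or neither (1 − p − d). A flip needs more than 2 responders at stage 1, exactly 7 in total, and 3–4 non-evaluable of 48 (or 1–2 of 46).

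| d | 23/48, p = 0.10 | 23/48, p = 0.25 | 23/46, p = 0.10 | 23/46, p = 0.25 | P(evaluable < 44, given 48 treated) |
|---|---|---|---|---|---|
| 2% | 0.4% | 0.2% | 3.7% | 2.0% | 0.3% |
| 5% | 2.4% | 1.0% | 3.6% | 1.6% | 9.1% |
| 10% | 2.7% | 0.7% | – | – | 53% |
| 15% | 1.0% | 0.2% | – | – | 87% |

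The flip probability falls at 15% because the evaluable count then usually drops below 44, where 11.3 gives no cutoff at all.

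**4. Type I error if n is filled with evaluable patients.** This is a separate scenario and should not be combined with step 3. If the 10% null describes treated patients and every responder is evaluable, the rate in the evaluable set is 0.10/(1 − d). Reaching 48 evaluable needs 48/(1 − d) treated.

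| d | Evaluable-set null | Average type I | At 23/48 | Treated needed |
|---|---|---|---|---|
| 0 | 0.1000 | 9.9% | 9.0% | 48 |
| 2% | 0.1020 | 10.7% | 9.9% | 49.0 |
| 5% | 0.1053 | 12.2% | 11.3% | 50.5 |
| 10% | 0.1111 | 15.1% | 14.1% | 53.3 |
| 15% | 0.1176 | 18.7% | 17.7% | 56.5 |

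The last two rows need about 54–57 treated patients, more than the synopsis maximum of 51, so they are unlikely to arise as written.

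**The case against.** The strongest reply is that 11.5 already settles the matter. It is the analysis-population rule, it removes only ineligible and untreated patients, and 11.3 builds unknown into non-response. On this view the phrase in 11.0 and 11.3 is shorthand for those two exclusions. The synopsis supports this reading: it expects 19–51 patients, exactly the stage limits, with no allowance for treated but non-evaluable patients. Section 6.1 also caps enrolled plus screening patients at total accrual. Section 8.1.6 assigns a response category to every included patient, even if not re-evaluated.

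It can also be said that the effect is small. Early progressors are evaluable, and scans continue after treatment stops (6.4, 8.1.4, 9.1.1), so few patients are affected. A flip needs exactly 7 responders. The 10.7–12.2% averages lie inside the 6.6–14.5% spread that the design already accepts, and at 23/48 with 2% non-evaluable the error is 9.9%, within the nominal 10%.

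Both points stand as limits. All eligible treated patients is the better-supported reading, and the numerical effect is modest. They do not remove the conflict. Section 11.5 never mentions stage counts or cutoffs, and the sections that do use a term whose only definition for response is narrower and begins by restricting membership. Excluding unknown patients would contradict 11.5, but including them would contradict the accrual wording read with 8.1.1.

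**Conclusion.** The concern holds: the plan is wrong as written, because its rules give two values of n for the same cutoffs. It should be fixed, although the expected effect is modest. At the 23/48 target the chance of opposite final conclusions is at most 2.7% over the assumed 2–15% non-evaluable; at 46 treated with 2–5% non-evaluable it is 1.6–3.7%. Filling n with evaluable patients moves average type I error from 9.9% to 10.7–12.2% at 2–5%. At stage 1 the conflict can change the cutoff only at the upper edge of accrual, not at the target of 23.

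These sizes rest on the assumed non-evaluable share, on excluded patients being non-responders, and on equal weighting of the 64 permitted sample-size pairs. That the two sets differ, and that the narrower one favours the regimen, follows from the text alone.

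**What to change.** In 11.0 and 11.3, replace the eligible-and-evaluable wording with eligible patients who received any study therapy, which is the 11.5 set. Use it for the stage counts, both sets of cutoffs and the 10% and 25% rates. State that anyone without a confirmed complete or partial response, including unknown, is a non-responder. Keep the 8.1.1 evaluable set for a sensitivity analysis only. Section 8.1.6 concerns the reporting of response categories and needs no change.

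The cost is a wording change and one added line. The reported response rate may be slightly lower. If the rates refer to treated patients, the stated 64%/10%/90% stand unchanged. If the 25% target was meant for evaluable patients (the less supported reading, since 11.3 puts unknown in non-response), the rate among treated patients is 0.25 × (1 − d). Average power would then be 88.8% at 2% non-evaluable, 86.8% at 5%, 82.8% at 10% and 77.9% at 15%, instead of 90.0%. The plan should say which population the 25% describes and disclose that loss if it applies.
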